10.6.7. Physical Examination

Physical Examination and ECG findings will be summarized. The shift from Screening to Visit 8 and Screening to the End-Study Assessment will be summarized. Body weight data will be fully listed.

10.6.8. Other Safety Parameters

Pregnancy test results will be listed.

10.7. Sensitivity Analyses

Sensitivity analyses will be performed to assess the impact on the primary PK analysis of non-compliers within the ITT population, missing primary endpoints, and timing of vaccine dosing.

10.7.1. Potential Interaction

Before treatment unblinding, timing of vaccine dosing at Visits 3-5 and PK sampling at visit 6, if not performed on the designated day, will be assessed as potential effect modifiers on the association between RVNA levels and treatment group in the primary PK analysis. A chi-square or fisher’s exact test, as appropriate, will be used to measure the association between the dichotomous indicator of receiving dose/PK sampling on the intended day [yes/no] and target level of RVNA titer reached [yes/no]. If the association is significant at the 0.05 level, a subgroup analysis including only subjects

who were dosed/sampled on the target day will be reported in addition to the full analysis.

10.7.2. Non-Compliers and Missing Data

Non-compliers will be defined as subjects who meet one of the following:

- subjects who did not receive the full dose of BPL HRIG/comparator HRIG [not eligible for primary PK population];
- subjects who did not receive the first 3 doses of active rabies vaccine at the time specified [not eligible for primary PK population];
- randomized without meeting all eligibility criteria [may be eligible for primary PK population];
- subjects with any major protocol deviations reported [may be eligible for primary PK population].

Specifically, the following two analyses will be performed to assess impact on primary PK analysis:

- The primary PK analysis will be repeated assuming that non-compliant subjects did not attain an RVNA titer of ≥ 0.5 IU/mL at Visit 6. [worst case scenario]
- The primary PK analysis will be repeated assuming that non-compliant subjects successfully attain an RVNA titer of ≥ 0.5 IU/mL at Visit 6. [best case scenario]

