10.4. Analysis Populations

The following analysis populations will be defined for this study.

Intent-to-Treat (ITT) Population

The intent-to-treat (ITT) population will include all randomized subjects. All analyses will be performed using the ITT population.

Safety Population

The safety population will be defined as all subjects who receive at least one dose of BPL HRIG / comparator HRIG. Safety data will be analyzed up to the point of withdrawal for applicable subjects. The safety population will be used for all safety analyses.

Per Protocol Population

The per protocol population will be split into the primary and secondary PK populations.

The **primary PK population** will be defined as all subjects who receive the full dose of BPL HRIG / comparator HRIG and the first 3 doses of active rabies vaccine on Visits 2, 3, and 5, and for whom the PK sample at Visit 6 is taken. This population will be used for the primary PK analysis and selected secondary analyses.

The **secondary PK population** will be defined as all subjects who receive the full dose of BPL HRIG / comparator HRIG and all 5 doses of active rabies vaccine and for whom all required PK samples are taken. This population will be used for selected secondary PK analyses and the exploratory PK analysis.

Subjects with a pre-dose RVNA of \geq the LLOQ will be excluded from all analyses.

Subjects not meeting eligibility criteria or for whom major protocol deviations are reported may be excluded from the per protocol population if considered to potentially impact on the PK analysis. Any such cases will be fully justified in the clinical study report.

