10.5.2. Hypothesis for the Primary PK Analysis

The null hypothesis is $p-p_0 \leq -0.1$;

The alternative hypothesis is $p-p_0 > -0.1$,

where p is the proportion of subjects with anti-rabies titer of ≥ 0.5 IU/mL at Visit 6 in subjects receiving BPL HRIG + vaccine and p_0 is the proportion receiving comparator HRIG + vaccine.

We reject the null hypothesis at the one-sided 0.025 significance level, and conclude that $p-p_0 > -0.1$, if the lower bound of an exact 95% binomial confidence interval exceeds -0.1.

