10.9. Determination of Sample Size

Statistical calculations indicate a minimum of 73 subjects per group is necessary. To allow for subject withdrawals or unevaluable data, approximately 81 subjects will be enrolled per group.

This study is powered based on a one-sided test with an overall study α of 0.05. A total of 162 subjects will be randomized to achieve 85% power with a one-sided significance level of 0.025.

This computation accounts for an expected 10% dropout rate resulting in 146 evaluable subjects. The following table outlines the underlying assumptions:

Table 7: The underlying assumptions

	Day 14 \geq 0.5 IU/mL
Non-inferiority margin	10%
Difference	0%
% success	98%

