[REDACTED] will be performing the RFFIT test and providing the results for data analysis. Subject serum will be tested in duplicates. If either individual test in duplicated set 1 fails QC, a second duplicate set of RFFIT tests will be run. The arithmetic mean value of the appropriate duplicate set, (set 1 if QC passed, set 2 if QC failed), will be used for the final reported rabies antibody titer [IU] for primary endpoint derivation. If the final arithmetic mean value is ≥ 0.5 IU/mL that subject-specific time point will be coded as 1 (success); otherwise if the final arithmetic mean value is < 0.5 IU/ml the time point will be coded as 0 (failure). If both duplicate sets fail the QC test,

the subject data is deemed non-evaluable. The proportion of subjects with RVNA titer ≥ 0.5 IU/mL is calculated as follows:

$$\frac{\sum(\text{successes}, 1)}{\sum(\text{all evaluable subject } i, n)}$$

Sensitivity analyses will be performed to assess impact of missing data, see section 8j.

f. SECONDARY EFFICACY ANALYSES

Secondary efficacy analyses 2 and 5 will be based on the secondary PK population. Secondary efficacy analyses 1, 3, and 4 will be based on the primary PK population, since timepoints post-Visit 6 are not included in these analyses.

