Specifically, the following two analyses will be performed to assess impact on primary PK analysis:

- The primary PK analysis will be repeated assuming that non-compliant subjects did not attain an RVNA titer of ≥ 0.5 IU/mL at Visit 6. [worst case scenario]
- The primary PK analysis will be repeated assuming that non-compliant subjects successfully attain an RVNA titer of ≥ 0.5 IU/mL at Visit 6. [best case scenario]

j. SUBGROUP ANALYSES

Subgroup analyses will be performed as appropriate, due to either imbalance randomization in baseline subject demographics and/or clinical relevance to primary and secondary PK analyses and safety analysis. Factors including, but not limited to, age, race, BMI, and sex will be considered. Subgroups will be defined based on population median.

K. MISSING VALUES

No missing value imputation methods will be applied, e.g. the analyses are based on a valid case basis.

I. INJECTION SITE OBSERVATIONS

Injection site observations data will be summarized as appropriate.

SUMMARY BY PRODUCT

The number and percentage of subjects reporting injection site reactions will be summarized by preferred term and product (HRIG or vaccine).

SUMMARY BY NUMBER OF INJECTIONS

The number and percentage of subjects reporting injection site reactions will be summarized by preferred term, product (HRIG or vaccine) and number of injections.

M. VIRAL SEROLOGY VARIABLES

Viral serology variables will be summarized. Shift tables for virology will present the number of subjects with positive and negative results and those for whom the results change during the study.

N. HEMATOLOGY, SERUM BIOCHEMISTRY, URINALYSIS

Hematology, serum biochemistry and urinalysis variables will be summarized, including changes from baseline. Shift tables for hematology and biochemistry variables will be provided for the number and percentage of subjects with values below, within and above the reference range.

O. MARKERS OF HEMOLYSIS

Markers of hemolysis will be summarized, including changes from baseline.

p. VITAL SIGNS AND BODY TEMPERATURE

Sitting diastolic and systolic blood pressure, pulse rate, body temperature and respiration rate will be summarized, including changes from baseline (i.e. pre-dose on Visit 2 for body temperature, Screening for all other parameters). In addition, the number of subjects with “substantial” increases or decreases from baseline in blood pressure (>20 mmHg) and pulse (>15 b.p.m.) will be summarized.

q. PHYSICAL EXAMINATION

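### The two sensitivity runs promised for missing primary endpoints reassign only non-compliant subjects, so a fully dosed subject with no usable Day 14 titer is in neither run unless reported as a major protocol deviation

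*Protocol*

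**What the plan says.** Protocol 10.7 gives the sensitivity analyses three targets: "non-compliers within the ITT population, missing primary endpoints, and timing of vaccine dosing". SAP 8.i repeats them. SAP 8.e, on deriving the primary endpoint, adds: "Sensitivity analyses will be performed to assess impact of missing data". It then points to section 8j, which is Subgroup Analyses; the sensitivity analyses are in 8.i.

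Protocol 10.7.2 is headed as covering both non-compliers and missing data. It defines a non-complier by four criteria: incomplete HRIG dose, first three vaccine doses not received as specified, failed eligibility, or a reported major protocol deviation. It then specifies two runs. The worst case reads "The primary PK analysis will be repeated assuming that non-compliant subjects did not attain an RVNA titer" of at least 0.5 IU/mL at Visit 6. The best case assumes that the same subjects did attain it. SAP 8.i has the same two runs.

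Two other rules decide who is counted. Protocol 10.4 limits the primary PK population to suitably dosed subjects "and for whom the PK sample at Visit 6 is taken". SAP 8.k states: "No missing value imputation methods will be applied, e.g. the analyses are based on a valid case basis".

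**The concern.** The stated purpose includes missing primary endpoints, but the group whose outcomes are reassigned is defined by dosing, eligibility and deviations, not by whether a Day 14 titer exists. Take a subject who receives full HRIG and vaccine on Days 0, 3 and 7 and then withdraws or misses Visit 6. That subject has a missing primary endpoint but meets none of the named dosing or eligibility criteria.

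If several such subjects occur, the run labelled worst case could equal the primary analysis, and a reader of the study report would take it as evidence that missing Day 14 data do not matter. In a non-inferiority comparison with an expected 98% success rate in both arms, a few failures shift the lower limit appreciably.

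**Working it through.** **1. The plan's own figure.** Inputs from Protocol 10.9: success 98% in both arms, margin 0.10, one-sided 0.025, power 85%. The Farrington-Manning formula is n = [(z_0.975 × s0 + z_0.85 × s1) / 0.10]². Here s0 uses the restricted estimates under a difference of -0.10 (0.8895 and 0.9895), so s0 = 0.3296, and s1 = √(2 × 0.98 × 0.02) = 0.1980. This gives n = 72.4, so 73 per group, as stated; power at 73 is 85.4%. Planned loss is 162 - 146 = 16, about 8 per arm.

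**2. Who is in which analysis (Day 14 responder comparison).**

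| Subject | Primary PK population | Worst/best-case runs |
|---|---|---|
| Withdrew before dose 3, or a dose withheld for fever on Day 3 or 7 | No | Yes, vaccine criterion |
| Fully dosed through Day 7, no Visit 6 sample | No | Only if reported as a major deviation |
| Fully dosed, both duplicate RFFIT sets fail QC | Non-evaluable, leaves the denominator (SAP 8.e) | Only if reported as a major deviation |
| Withdrew after Day 14, sample taken | Yes | Not needed |

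An ITT responder comparison does not recover rows 2 and 3, because SAP 8.k keeps it to valid cases.

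**3. Size.** The documents do not split the 16 losses by timing, so the count in rows 2 and 3 is taken as 0 to about 8 per arm. Assumptions: 81 randomized per arm, one observed failure per arm, no other non-compliers, no pre-dose exclusions. The lower limit is the value d at which (p_BPL - p_comparator - d) / SE(d) = 1.96, with SE from the restricted estimates under d.

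With 8 missing per arm, the analysis as written is 72/73 v 72/73: lower limit -6.1%, one-sided p = 0.004. The written worst case is identical, since nobody is a non-complier. Counting missing titers as failures gives:

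| Missing, BPL v comparator | Counts | Lower limit | -10% margin |
|---|---|---|---|
| 2 v 2 | 78/81 v 78/81 | -7.1% | met |
| 4 v 4 | 76/81 v 76/81 | -8.3% | met |
| 7 v 7 | 73/81 v 73/81 | -9.8% | met |
| 8 v 8 | 72/81 v 72/81 | -10.2% (p = 0.027) | not met |
| 3 v 2 | 77/81 v 78/81 | -8.8% | met |
| 4 v 3 | 76/81 v 77/81 | -9.4% | met |
| 3 v 1 | 77/81 v 79/81 | -9.9% | met |
| 4 v 2 | 76/81 v 78/81 | -10.5% (p = 0.031) | not met |

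**4. Chance that the extended worst case meets the margin.** With 98% success among observed subjects and missing counted as failure, exact enumeration of the score test on 81 per arm gives 92% with none missing, 77% with 2.5% missing, 65% with 5% and 48% with the full 10%.

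**The case against.** The best counter-argument is that the runs were plainly meant to cover these subjects, as the section heading and 10.7 show, and that the fourth criterion lets them in if a missed Day 14 sample is reported as a major deviation. That route exists, so a reader who infers that such losses can never be tested goes too far. It is not pre-specified, however. The visible text of neither document defines a major deviation, and Protocol 9 lists withdrawal of consent and loss to follow-up separately from significant protocol deviation. Some SAP text near these definitions is redacted, but the Protocol's own list is complete and has no missing-titer criterion.

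A reader might also infer that these subjects enter no analysis at all. That is not so. They are in the safety population, and their Day 3, 5 and 7 titers can be used in ITT repeated-measures analyses. Only the Day 14 responder comparison loses them.

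Assay failure is largely handled. SAP 8.e runs a second duplicate set, and Protocol 7.9.1 keeps two reserve samples per timepoint for re-analysis. Neither helps when the visit did not happen.

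Eight per arm is an extreme bound. It puts the whole allowance, which also covers unevaluable data, into the week between Days 7 and 14, although earlier withdrawals are already covered and later ones keep their endpoint. Most of the smaller cases tabulated still meet the margin.

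Finally, one might infer that the non-inferiority claim depends on these runs. Protocol 10.5.1 rests it on the primary PK population alone.

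**Conclusion.** The point holds as a gap between a stated purpose and the analyses specified to meet it. Followed literally, the plan gives a worst case that omits fully dosed subjects without an evaluable Visit 6 titer, apart from any reported as major deviations. In practice these are mainly withdrawals or missed samples between Day 7 and Day 14.

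The effect depends on a number that the documents do not give. Under the assumptions above, equal losses overturn the worst case only at 8 per arm, the edge of the planned allowance. Unequal losses do so sooner: 4 v 2 fails, while 3 v 2, 4 v 3 and 3 v 1 pass. The validity of the primary analysis is not in question. What is affected is what the sensitivity analyses can be said to show about missing Day 14 data. The change should be made before unblinding.

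**What to change.** In Protocol 10.7.2 and SAP 8.i, apply both runs to non-compliant subjects and to all other randomized subjects without an evaluable Visit 6 RVNA result: withdrawn before Visit 6, sample not taken, or no valid assay result after repeat and reserve testing. Use as denominator all randomized subjects except those with pre-dose RVNA at or above the LLOQ, whom Protocol 10.4 and SAP 7.b exclude from all analyses. State in SAP 8.k that the runs in 8.i are exempt from the no-imputation rule. Correct the SAP 8.e pointer from 8j to 8i.

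Both runs give missing subjects the same outcome in each arm. An added run with missing BPL titers as failures and missing comparator titers as successes would bound the effect of differential loss; it is optional.

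The cost is a few sentences of wording and a reported worst case that may be less favourable. No new data are needed, and the primary analysis and sample size do not change.

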8. OUTCOME MEASURES

8.1. Efficacy Measures

8.1.1. Primary efficacy endpoint

The primary efficacy endpoint is to demonstrate non-inferiority of BPL HRIG compared to an FDA-licensed HRIG product, in terms of:

- the proportion of subjects with anti-rabies antibody titer of ≥ 0.5 IU/mL on day 14 after administration of BPL HRIG and vaccine / active comparator and vaccine using a non-inferiority margin 10%.

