10.5.1. Primary PK Analysis

The primary efficacy analysis will be based on the primary PK population.

The primary hypothesis is that the proportion of subjects receiving BPL HRIG + active vaccine with an anti-rabies titer of ≥ 0.5 IU/mL will not be less than the corresponding proportion for subjects receiving comparator HRIG + active vaccine, by more than 0.1 at Visit 6. The Farrington and Manning test statistic will be used to assess the statistical comparison at a one-sided significance level of 0.025. It will be concluded that the BPL HRIG is non-inferior to the comparator HRIG if the lower limit of an exact binomial 95% confidence interval calculated from the Farrington-Manning score test is greater than the *a priori* set -10% non-inferiority margin.

An additional analysis will be performed to assess the impact of dosing/PK sampling not being performed on the designated day. See Section 10.7.2.

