4. STUDY DESIGN

This will be a prospective, randomized, double-blind, parallel-group, non-inferiority, phase II/III study of the safety and effectiveness of simulated post-exposure prophylaxis with BPL HRIG with co-administration of active rabies vaccine in healthy subjects. This is intended to be a multi-center study. Treatment assignment is blinded until post database lock.

Subjects will be randomized 1:1 to one of the 2 treatment groups, as follows:

HRIG treatment	Rabies vaccine treatment	# of Subjects
BPL HRIG	active rabies vaccine	81
comparator HRIG	active rabies vaccine	81

Prior to randomizing a participant, all screening and baseline evaluations must be completed and the participant determined to be eligible for inclusion in the study. Randomization and the baseline visit (Day 0) should occur no later than 28 days after the completion of the screening visit.

All medicinal product preparation will be performed by the site pharmacist using aseptic techniques and according to a standardized procedure on Day 0, and administration of HRIGs + vaccine will be administered an unblinded nurse administrator. All study assessments and Post Day 0 treatment administration will be performed by blinded study personnel. Investigators and subjects will be blinded to treatment assignment.

Subjects will be identified by a unique five-digit number as follows: each site will be allocated a two-digit site number (e.g. Site 01, etc) and each subject will be allocated a three-digit subject number (e.g. 001) at the Screening Visit. Each subject will be identified by the unique site and subject number combination (e.g. 01001).

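### The worst-case and best-case runs give every non-complier an assumed Day 14 outcome, even where a titer was measured, and leave out compliant subjects whose titer is missing

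*Protocol*

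**What the plan says.** Protocol 10.7 says the sensitivity analyses will assess how the primary analysis is affected by non-compliers in the ITT population, by missing primary endpoints and by the timing of vaccine doses.

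Protocol 10.7.2 defines four kinds of non-complier:

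1. HRIG dose not given in full.
2. First three vaccine doses not received at the time specified.
3. Randomized without meeting all eligibility criteria.
4. "subjects with any major protocol deviations reported [may be eligible for primary PK population"].

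The third kind carries the same bracketed remark as the fourth. The first two are marked as not eligible for the primary PK population.

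The analysis is then "repeated assuming that non-compliant subjects did not attain an RVNA titer of" 0.5 IU/mL or more (worst case), and repeated with all of them counted as successes (best case). SAP 8.i does the same, in the best case "assuming that non-compliant subjects successfully attain an RVNA titer" at or above the threshold. Neither document limits the assumption to subjects without a titer.

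Three other rules bear on this. Protocol 10.4 admits a subject to the primary PK population only if the Visit 6 sample was taken. The same section promises all analyses in the ITT population. SAP 8.k says that no imputation of missing values will be applied.

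**The concern.** Worst-case and best-case assignments are bounds for outcomes nobody knows. Here they are applied to a group defined by conduct, and some of that group will have known outcomes. The worst case then discards observed successes and the best case erases observed failures.

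Because both arms receive the same assumed value, a product that did worse among non-compliers would look the same as the comparator in that group. That difference is part of what 10.7 sets out to examine. The other target in 10.7, missing primary endpoints, is reached only when a subject with a missing titer also happens to be a non-complier.

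At stake is how the two named sensitivity runs are read. They could reassure when the measured data would not, or alarm when the products are identical.

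**Working it through.** **Inputs.**
- Margin: 10 percentage points (Protocol 8.1.1, "using a non-inferiority margin 10"%).
- Test: "The Farrington and Manning test statistic will be used to assess the statistical comparison at a one-sided significance level of 0.025" (Protocol 10.5.1).
- Size: "A total of 162 subjects will be randomized to achieve 85% power with a one-sided significance level of 0.025" (Protocol 10.9); "Subjects will be randomized 1:1 to one of the 2 treatment groups" (SAP 4), so 81 per arm.
- Assumed success rate: 98% with no difference (Protocol 10.9).
- Number of non-compliers: not in the documents, so assumed and varied below.

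**1. The plan's own figure.** The Farrington-Manning sample size is n = [(z₀.₉₇₅·s₀ + z₀.₈₅·s₁)/0.10]². The restricted null rates at 98% vs 98% are 0.8895 and 0.9895.
- s₀ = √(0.8895×0.1105 + 0.9895×0.0105) = 0.3296
- s₁ = √(2×0.98×0.02) = 0.1980
- n = [(1.960×0.3296 + 1.036×0.1980)/0.10]² = 72.4, rounded up to 73

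This agrees with "Statistical calculations indicate a minimum of 73 subjects per group is necessary". Also 162 × 0.9 = 145.8, the stated 146 evaluable.

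**2. Who can have a measured titer and still be overwritten.**

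| Non-complier category | Can a Visit 6 titer exist? |
|---|---|
| Incomplete HRIG dose | Yes, if the subject stays in the study |
| First three vaccine doses not as specified | Yes. For example, Protocol 7.4.1 lets a febrile subject continue without further vaccine |
| Eligibility breach | Yes. Anyone kept in the primary PK population has a Visit 6 sample by definition |
| Major deviation | Yes, for the same reason |

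The SAP's bracketed remarks on the last two categories are blacked out, so this step rests on the protocol.

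**3. Illustration (assumed counts).** Each arm has 75 compliers, 74 of them successes, and 6 non-compliers with measured titers. Among the non-compliers, 2/6 succeed on BPL HRIG and 6/6 on comparator. The lower limits come from the score test.

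| Analysis | BPL HRIG | Comparator | Lower 95% limit | Non-inferior? |
|---|---|---|---|---|
| Measured titers kept | 74+2 = 76/81 | 74+6 = 80/81 | -12.6% | No |
| Worst case as written | 74+0 = 74/81 | 74+0 = 74/81 | -9.3% | Yes |
| Best case as written | 74+6 = 80/81 | 74+6 = 80/81 | -5.5% | Yes |

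**4. Chance of passing.** All binomial outcomes at 81 per arm were enumerated under the score test. Each subject is overwritten with assumed probability q.

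Worst case, both arms truly 98%: each arm's success rate becomes 0.98(1−q).
- q = 0: 0.980, passes 92%
- q = 0.05: 0.931, passes 65%
- q = 0.10: 0.882, passes 48%

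Best case, truth at the margin (88% vs 98%): the rates become 0.88(1−q)+q and 0.98(1−q)+q.
- q = 0: 0.880 vs 0.980, wrongly passes 2.1%
- q = 0.05: 0.886 vs 0.981, 2.8%
- q = 0.10: 0.892 vs 0.982, 3.7%

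With fixed rather than random counts, the worst case passes 77.5% of the time at 4 per arm and 42.8% at 8 per arm. With unequal counts it passes 5.5% at 6 BPL vs 2 comparator, and 99.3% at 2 vs 6. The result follows how many subjects are labelled non-compliant in each arm, not what their titers were.

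**5. Missing endpoints.** SAP 8.e makes a subject non-evaluable if both duplicate assay sets fail quality control. Such a subject, if otherwise compliant, meets none of the four definitions and enters neither run. The same holds for a compliant subject with no Visit 6 sample, unless the missed sample is itself logged as a major deviation.

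**The case against.** The strongest defence has four parts.

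**Non-compliance as failure is a recognised severe approach.** Protocol 10.7 names non-compliers as a target separate from missing endpoints. A worst case that can fail for identical products is behaving as a stress test. This stands in part. A reader might infer that neither run tests robustness at all, and step 4 does not support that: the worst case imposes real stress. It does not bound the between-arm difference, however, and the mirror-image success run has no such rationale.

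**The measured titers are not lost.** The promised ITT analysis, on a valid-case basis, would show them alongside the two scenarios. This stands as mitigation. It does not repair the two named runs.

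**Late doses may not count.** A reader might infer that one dose given a day late is enough to be overwritten, since Days 3, 7 and 14 carry no visit window. The documents do not settle this. The criterion covers only the first three doses (Days 0, 3 and 7), so the Day 14 dose is outside it. Protocol 10.7.1 examines off-day dosing within the primary PK analysis, and SAP 7 uses visit labels regardless of actual timing. Both suggest that the time specified means the visit. The point does not depend on the late-dose reading.

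**The numbers depend on assumed counts.** They do. Nor do the documents show that most non-compliers will have a titer, only that some can. The best-case inflation is small at plausible shares.

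**Conclusion.** The concern holds in this form: as written, both runs replace measured Visit 6 results for any non-complier who has one, assign the same value in both arms, and omit compliant subjects without an evaluable titer.

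The illustration shows that both runs can pass while the measured data fail by 2.6 points beyond the margin. It shows what is possible, not what is likely. In the other direction, identical products at 98% would pass the worst case 65% or 48% of the time instead of 92%, if 5% or 10% of each arm were overwritten. Those shares are assumptions. The percentages use the score test at its usual critical value; the exact limit the plan also mentions could move them by a few points.

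These are supporting analyses. The primary analysis and sample size are unaffected, and neither run decides non-inferiority. The change should be made before unblinding.

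**What to change.** In Protocol 10.7.2 and SAP 8.i:

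1. Use the measured Visit 6 titer for every randomized subject who has an evaluable one, compliant or not.
2. Assume failure or success only where no evaluable Visit 6 titer exists, whatever the reason, including failed assay quality control.
3. Add a directional run in which missing BPL HRIG subjects are failures and missing comparator subjects are successes. Without it, both arms still receive the same assumed value and the difference is not bounded. Present it as a bound, not a decision rule: with 4 such subjects per arm and both arms truly 98%, it passes only 12.4% of the time.
4. In SAP 8.k, except these runs from the no-imputation rule.

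The cost is a few sentences across the two documents and one extra run. No new data are needed.
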